## 4. Efficacy Evaluation

### 4.1 Primary Efficacy Endpoint

#### 4.1.1 Definition

The primary endpoint concerns a safety endpoint. There is no primary efficacy endpoint.

#### 4.1.2 Analysis Methods

Not applicable.

### 4.2 Secondary Efficacy Endpoints

#### 4.2.1 Definition

Within-participant HSV-2 DNA detection rate on days with asymptomatic shedding For each person, the number of swabs on which shedding occurs only pre-intervention will be assessed, and then the number of swabs on which shedding occurs only postintervention will be subtracted. It will be tested whether the number of swabs on which shedding occurs only pre-intervention is the same when compared to the number of swabs on which shedding occurs only post-intervention.

HSV-2 copy number on HSV DNA positive samples detected by quantitative real-time PCR For each person, the mean PCR HSV-2 copy number on days with asymptomatic shedding occurring only pre-intervention will be calculated, and then the mean PCR HSV-2 copy number on days with asymptomatic shedding occurring only post-intervention will be subtracted. It will be tested whether the HSV-2 copy number on which shedding occurs only pre-intervention is the same when compared to the HSV-2 copy number on which shedding occurs only post-intervention.

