9.5.2. Secondary Endpoints

Secondary endpoints with respect to device performance are:

- Within-participant HSV-2 DNA detection rate on days with asymptomatic shedding
- HSV-2 copy number on HSV DNA positive samples detected by quantitative real-time PCR on days with asymptomatic shedding

The secondary endpoint with respect to safety is:

- Total number and type of AEs after minimally 26 days of VIBLOK use.

Secondary analyses will be performed in the AT population. The analyses will be repeated for the PP population.

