#### Secondary endpoints with respect to device performance

Within-participant HSV-2 DNA detection rate on days with asymptomatic shedding. For each person, the number of swabs on which shedding occurs only pre-intervention will be assessed, and then the number of swabs on which shedding occurs only postintervention will be subtracted. The following hypothesis will be tested:

$H_0$ : The number of swabs on which shedding occurs only pre-intervention is the same when compared to the number of swabs on which shedding occurs only post-intervention

$H_1$ : The number of swabs on which shedding occurs only pre-intervention is not the same when compared to the number of swabs on which shedding occurs only post-intervention

HSV-2 copy number on HSV DNA positive samples detected by quantitative real-time PCR on days with asymptomatic shedding will be tested using the following hypothesis:

$H_0$ : The HSV-2 copy number on which shedding occurs only pre-intervention is the same when compared to the HSV-2 copy number on which shedding occurs only post-intervention

$H_1$ : The HSV-2 copy number on which shedding occurs only pre-intervention is not the same when compared to the HSV-2 copy number on which shedding occurs only post-intervention

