### 2.3 Missing values and outliers/ implausible measurements

Missing values will not be replaced in the statistical analysis.

An investigation may be done concerning the sensitivity of the results of analysis to the method of handling missing values, especially if the number of missing values is substantial.

Assessments directly measured by the participant will not be subject to a reconciliation process.

Therefore, implausible measurements as described in the table below might be removed from the statistical analysis. However, the implausible measurements will be presented in individual data listings. Final decision whether or not to remove implausible measurements from the statistical analysis will be documented in the Exclusion Memo.

| Parameter | Implausible measurements                |
|-----------|---|
| Swab data | Before/after assessment                 |
| Swab data | Obvious mistake in date on the swab log |
|           |   |

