##### HSV-2 copy number on HSV DNA positive samples detected by quantitative real-time

The difference of the mean PCR HSV-2 copy number on days with asymptomatic shedding occurring only pre-intervention and occurring only post-intervention will be compared to zero using the non-parametric Wilcoxon signed-rank test.

Both analyses will be based on the As Treated Population and repeated for the Per Protocol Population.

Exploratory Poisson regression analyses may also be performed exploring the effect of other covariates like center, age and gender.

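### The SAP's copy-number test uses only days when one swab is positive and the other negative, so it does not measure a fall in copy number and runs out of data when the cream works

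*SAP*

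**What the plan says.** The protocol compares HSV-2 copy number before and after the cream on days with asymptomatic shedding (Protocol 3.2). Protocol 9.5.2 defines the endpoint as "HSV-2 copy number on HSV DNA positive samples detected by quantitative real-time PCR on days with asymptomatic shedding", and Protocol 9.6 refers to the mean copy number on positive samples. Neither is limited to days when only one swab is positive.

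The SAP adds that limit in three places:

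- **SAP 1.3 (null hypothesis):** "The HSV-2 copy number on which shedding occurs only pre-intervention is the same when compared to the HSV-2 copy number" on days with shedding only after the cream.
- **SAP 4.2.1 (definition):** "For each person, the mean PCR HSV-2 copy number on days with asymptomatic shedding occurring only pre-intervention will be calculated". From this the participant's corresponding average over post-only days is taken away.
- **SAP 4.2.2 (analysis):** the two means "occurring only pre-intervention and occurring only post-intervention will be compared to zero using the non-parametric Wilcoxon signed-rank test".

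In the neighbouring detection-rate endpoint the same wording plainly means discordant swabs: pre-only days minus post-only days. No rule covers a participant who has none of one kind of day. SAP 2.3 says "Missing values will not be replaced in the statistical analysis". No scale is named for the mean, so as written it is a mean of raw copies.

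**The concern.** The pre-only/post-only rule is right for counting discordant swabs, where concordant days carry no information. It does not suit a quantitative comparison, for four reasons.

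1. On a both-positive day the assay returns a copy number before and after the cream, at the same site and 5 to 60 minutes apart. These days are left out.
2. The pre mean and the post mean are taken over different days. The pairing that the daily two-swab design was built to give is lost.
3. A barrier that works makes post-only days rare. The participants left in the test are those who had at least one.
4. On the raw scale, one high-copy day can dominate a participant's mean.

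This is one of only two performance endpoints with a hypothesis test, in a study meant to support CE marking. A non-significant result could be read as no effect on viral quantity when the test simply had almost no data. Choosing a remedy after seeing the swab results would be post hoc.

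**Working it through.** **Inputs.** SAP 1.4 gives 8% asymptomatic shedding, a 50% reduction (so 4% after the cream), 40 participants and 28 days. The 40 is sized for the detection-rate test. The documents give no sample size or power for the copy-number test, so there is no figure of the plan's own to reproduce. They also do not say how often both swabs are positive on the same day, so I vary that.

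**Evaluable participants at the planned effect.** Let *c* be the share of days with both swabs positive. Pre-only days have probability *a* = 8% − *c*, and post-only days *b* = 4% − *c*. A participant is evaluable with at least one of each in 28 days. With independent days and no between-person variation:

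P = 1 − (1−a)^28 − (1−b)^28 + (1−a−b)^28

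| Overlap of the two swabs | c | a | b | P | Of 40 |
|---|---|---|---|---|---|
| Independent (8% × 4%) | 0.32% | 7.68% | 3.68% | 1 − 0.107 − 0.350 + 0.034 = 57.7% | 23 |
| Half of post-positive days | 2% | 6% | 2% | 1 − 0.177 − 0.568 + 0.097 = 35.2% | 14 |
| Three quarters | 3% | 5% | 1% | 1 − 0.238 − 0.755 + 0.177 = 18.4% | 7 |
| All (nested) | 4% | 4% | 0% | 0% | 0 |

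Independence is the favourable extreme, because two swabs of the same site within an hour should agree more often than chance. Simulation agrees with these counts. Strong between-person variation (beta distribution, shape 0.5) lowers 23 to about 15 and 14 to about 11.

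**Larger effects.** Simulated evaluable participants out of 40, without between-person variation:

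| Reduction in detection | 0% | 25% | 50% | 75% | 90% | 98% |
|---|---|---|---|---|---|---|
| Independent | 31.1 | 28.3 | 23.0 | 14.4 | 6.7 | 1.5 |
| Half overlap | 18.5 | 17.3 | 14.1 | 8.3 | 3.7 | 0.8 |
| Nested | 0 | 0 | 0 | 0 | 0 | 0 |

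The protocol synopsis cites up to 98% blocking in bench and animal work. The smallest two-sided exact signed-rank p-value with *n* non-zero differences is 2/2^n: 0.0625 for *n* = 5 and 0.031 for *n* = 6. With fewer than six evaluable participants the test cannot reject at 5%.

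**Copy-number simulation.** Assumed, since the documents give none of it: true log10 copies with mean 4 and SD 1.5, swab noise SD 0.5 or 1.0, detection limit 2 log10, 40 participants, 28 days. The comparator is a paired analysis of all days with at least one positive swab.

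| True fall (log10) | Noise SD | Pre-only / post-only / both-positive days | Evaluable, SAP rule | SAP test rejects | Paired analysis rejects |
|---|---|---|---|---|---|
| 0 | 0.5 | 2.9 / 2.9 / 77.2 | 0.2 | 0% | 4.6% |
| 0.5 | 0.5 | 7.4 / 1.2 / 72.8 | 0.2 | 0% | 99.9% |
| 0.5 | 1.0 | 10.5 / 4.4 / 67.5 | 0.9 | 0% | 75.8% |
| 1.0 | 1.0 | 16.7 / 2.8 / 60.6 | 0.9 | 0% | 99.9% |
| 2.0 | 1.0 | 33.7 / 0.9 / 43.9 | 0.5 | 0% | 100% |

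Pre-cream positivity in the second row is (7.4 + 72.8)/(40 × 28) = 7.2%, close to the SAP's 8%. The share of positive days discarded there is 72.8/(7.4 + 1.2 + 72.8) = 89%. In the last row it is 43.9/(33.7 + 0.9 + 43.9) = 56%. The paired analysis keeps about 35 of 40 participants.

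A second assumed model (10–11% pre-cream positivity, SD 1.3, limit 150 copies, between-participant ICC 0.2) gave the same picture for falls of 0.5 to 2 log10. It discarded 49–91% of positive days, left at most 3.3 evaluable participants, and gave the SAP test at most 5% power against about 80–100% for the paired analysis.

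**The case against.** **The loss of participants is inferred.** SAP 2.3 speaks of missing values, not of a mean over zero qualifying days, and SAP 2.9 defers incomplete data to a separate plan. This stands as a qualification. The other obvious convention, setting an absent mean to zero, gave roughly 37–100% power in a small simulation (60 replicates). But the sign of most differences would then depend only on which kind of discordant day the participant had. That largely repeats the detection-rate endpoint, and both-positive days would still be excluded.

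**The size depends on the model.** This also stands. With independent swabs about 23 of 40 remain at the planned effect, which is not a handful. Near-zero counts need concordant swabs or a large effect. Under nesting the test is empty at every effect size, and in the simulation with noise SD 1.0 the evaluable count first rises slightly (0.78 to 0.93) before it falls. The paired analysis is not always strong either: a small run with positivity near 8% gave about 62% power at 0.5 log10.

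**The remedy goes beyond positive samples.** Giving undetectable swabs a fixed value brings some detection information into the endpoint and needs a limit the documents do not state. But using both-positive days alone would drop every fall to below the limit and so understate the effect. Protocol 3.2 asks for before and after on shedding days, which the paired definition answers.

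**The endpoint is secondary.** Study success rests on the SADE upper limit, and the detection-rate test is unaffected. SAP 4.3.2 also shows pre/post differences descriptively. None of this makes the stated test answer its question.

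**Conclusion.** The concern holds. Three consequences follow from the SAP text alone: both-positive days enter neither mean, the two means come from different days, and a participant lacking either a pre-only or a post-only day has no defined difference. The SAP also narrows the protocol's endpoint without saying so.

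The size rests on assumptions about same-day overlap, between-person variation, copy-number distribution, swab noise and detection limit, and on undefined differences being left out of the test. Within those, 0 to 23 of 40 participants are evaluable at the planned effect. With 98% blocking, fewer than two are evaluable. In the copy-number models examined, the SAP test has between 0% and 5% power for true falls of 0.5 to 2 log10. The paired analysis has roughly 62% to over 99% at 0.5 log10 and close to 100% for larger falls. The definition must be corrected before the swab data are analysed.

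**What to change.** Amend SAP 1.3, 4.2.1 and 4.2.2:

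- For each asymptomatic day with both swabs available and at least one positive, compute log10(pre copies) − log10(post copies).
- Set an undetectable swab to one fixed value at or below the assay's detection limit, obtained from the core laboratory and written into the SAP.
- Average within participant and test the averages against zero with the two-sided Wilcoxon signed-rank test.
- State that participants with no qualifying day are not evaluable, and report how many there are.
- Report both-positive days alone as a supportive analysis.

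Substituting a fixed value shrinks large effects: in the simulation a true fall of 2 log10 averaged about 1.6. The estimate should be described accordingly.

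The cost is SAP wording and programming. No new swabs, visits or participants are needed.

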Background	
Genital herpes has a high prevalence in industrialized as well as developing countries.
 
Genital herpes causes genital ulcers, increases risk for acquiring HIV infection, and may be transmitted mother to child during birth with possible serious consequences.
 
Medical treatments and condoms only partially reduce the risk for transmission from/ to sexual partners. Genital herpes transmission despite use of condoms is thought to be due to transfer via skin-to-skin contact in unprotected areas, and HSV-2 transmission may be enhanced by current shaving habits in the genital area leading to micro lesions (lacerations) of the skin.
 
VIBLOK™ is a cream designed to impede the passage of viruses, such as HSV-2, across the skin. Bench and animal experiments indicate that it can block virus transmission (HIV, HPV, HSV) up to 98%.
 
The objective of this clinical trial is to assess the safety and performance of VIBLOK in adults with HSV-2 infection by comparing virus detection in the extra-genital area before and after application of the barrier cream.

Primary objective	To assess safety of VIBLOK in HSV-2 infected adults.
Secondary objective	To evaluate the performance of VIBLOK as a barrier for virus transmission in men and women.
Study design	The VIBLOK SAfety and perFormancE Trial is a prospective, non-randomized, comparative multi-center safety and performance study. Up to 84 adults with a suspected HSV-2 infection are planned to be enrolled at up to 6 participating investigational centers in The Netherlands and Germany. Participants with a confirmed HSV-2 infection are planned to be followed for 26-31 days, using VIBLOK for minimally 26 days in a row. Safety will be assessed by collecting all adverse events, and HSV will be measured from daily self-collected external genital swabs before and after application of VIBLOK.
Study device	VIBLOK cream
Study scope	Minimally 1 and maximally 6 sites in The Netherlands and Germany are

	planned to participate in this study.
Study duration	The study is anticipated to last 12 months from first-subject-in to last-subject-out. Study participants are planned to be followed for 26 to 31 days.
Study Population	Adults with recurrent genital HSV-2 infections that meet all the inclusion and none of the exclusion criteria.
Number of subjects	Up to 84 men and women are to be enrolled, ensuring 46 participants with confirmed eligibility applying VIBLOK.

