9.6. Endpoint Analysis

All statistical analyses will be performed by CLJI or a designee. Participant data listings and tabular and graphical presentations of results will be provided. All clinically relevant baseline and follow-up variables will be tabulated. Descriptive statistics will be used for continuous variables (e.g., mean, standard deviation, sample size, minimum, and maximum) and frequency tables or proportions for discrete variables.

Swab samples will be analyzed by a core laboratory for HSV DNA and the mean HSV-2 copy number on HSV-2 DNA positive samples.

Further details of the statistical methods will be provided in the Statistical Analysis Plan.

10. Study Administration

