#### 1.4 Sample size justification

The primary endpoint is the SADE incidence at 28 days of VIBLOK usage.

With a sample size of 36, an exact two-sided 95% confidence interval for a single proportion will show that the SADE incidence is below 10% at an expected incidence of 0.1%. Taking into account a drop-out rate of 15%, the estimated sample size needed is 42 study participants applying the VIBLOK cream.

The secondary endpoint is VIBLOK performance.

Statistical analysis will evaluate whether the disagreement rate in positivity between the pre and post-treatment swabs is indicative of a decrease in detection frequency. For each person, the number of swabs on which shedding occurs only pre-intervention will be assessed, and then the number of swabs on which shedding occurs only post-intervention will be subtracted.

If this number averages above zero, it indicates that the detection rate is decreased following intervention, and therefore a protective effect of the intervention with regard to shedding. Since this number is not distributed according to a known distribution, it will be compared to zero using a non-parametric test, the Wilcoxon signed-rank test. With an 8% anticipated asymptomatic shedding rate, 80% power and type I error of 5%, 40 participants taking samples for 28 days are needed to show a 50% reduction post-intervention, i.e. after applying VIBLOK.

Taking into account a drop-out rate of 15%, up to 46 adults applying VIBLOK cream are needed.

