#### **2.8 General Issues For Statistical Analyses**

Descriptive statistics (N, Mean, Median, STD, min, Max) will be presented for continuous data, frequencies and percentages will be presented for categorical variables. Continuous, non-normally distributed variables will be analyzed using the nonparametric Wilcoxon signed-rank (within group comparisons) test or Wilcoxon rank-sum test (between group comparisons). The latter will be accompanied by Hodges-Lehmann estimates (point estimate and 95% exact confidence interval) to assess the location of the shift between groups. Twosided exact 95% Clopper-Pearson confidence intervals will be calculated for categorical variables. Hypotheses will be tested two-sided using an alpha-level of 5%.

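### HSV-2 copy number is averaged per person on the raw scale; once the set of days is settled, mean log10 copies would test a proportional reduction with more power

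*SAP*

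**What the plan says.** SAP 4.2.1 defines the per-person summary: "For each person, the mean PCR HSV-2 copy number on days with asymptomatic shedding occurring only pre-intervention will be calculated". It continues that "the mean PCR HSV-2 copy number on days with asymptomatic shedding occurring only post-intervention will be subtracted". SAP 4.2.2 then has this difference "occurring only post-intervention will be compared to zero using the non-parametric Wilcoxon signed-rank test". SAP 2.8 sets two-sided tests at the 5% level.

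Protocol 9.6 has the core laboratory deliver "the mean HSV-2 copy number on HSV-2 DNA positive samples" and leaves further methods to the SAP. No log transform, geometric mean or per-person median appears in either document. The median and rank test in SAP 2.8 operate across participants, after each person's swabs have been averaged.

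Two other passages bear on the point:
- The Study Synopsis (Background) describes the device effect as a proportion: "Bench and animal experiments indicate that it can block virus transmission (HIV, HPV, HSV) up to 98" percent.
- Protocol 9.5.2 places the copy-number endpoint on positive samples from days of asymptomatic shedding. SAP 1.3, 4.2.1 and 4.2.2 narrow it to days positive on one side of application only.

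Neither document gives an SD, an expected reduction, a power figure or a detection limit for copy number.

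**The concern.** A cream that blocks a given percentage of virus acts multiplicatively. An arithmetic mean of copies does not follow that kind of effect well when a person's values range over powers of ten. As an illustration with assumed values, take swabs of 10^3 and 10^5 copies. The arithmetic mean is (1,000 + 100,000)/2 = 50,500, and the larger swab supplies 100,000/101,000 = 99% of the sum. The mean of the logs is (3 + 5)/2 = 4, or 10,000 copies, and both days count equally.

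The signed-rank test does not undo this. It ranks the absolute differences across people, and those differences scale with how much each person sheds. A small fraction blocked in a heavy shedder can outrank a large fraction blocked in a light one.

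At stake are the precision of one of the two performance endpoints, which are meant to support CE marking, and whether its result can be read as a percentage reduction.

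**Working it through.** **The plan's own figure.** The only performance sizing (Protocol 9.1, SAP 1.4) is for the detection rate: "With an 8% anticipated asymptomatic shedding rate, 80% power and type I error of 5" percent, 40 participants, 28 days, 50% reduction. It cannot be reproduced exactly, because between-person variation in shedding and before/after discordance are not given. Simulated detection-rate power at 40 participants, with independent before and after detection, runs from 97% (no heterogeneity) to 79% (coefficient of variation 3). There is no figure to reproduce for copy number, so I borrow 40, 28 days, 8% and 50% as design inputs.

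**How many swabs each person contributes.** Expected positive days are 0.08 × 28 = 2.24. Assume shedding rates follow a beta(0.8, 9.2) distribution, mean 0.8/10 = 8%. Then P(no shedding day) = 0.325 and P(exactly one) = 0.201.
- Contributing participants: 40 × (1 − 0.325) = 27.0.
- Shedders with a single day: 0.201/(1 − 0.325) = 30%. Averaging on either scale returns that one swab.
- Among people with two or more positive pre swabs, the largest carries on average 62–82% of the raw sum (assumed between-day SD 0.5–1.5 log10).

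**Power.** Assumed model: log10 copies = person level + day level + swab noise, all normal. The effect is a shift of log10(0.5) = −0.30 after application. Each person's difference is computed from raw means or from log10 means and tested by a two-sided 5% signed-rank test, with 600–1,500 simulated trials per setting. All SDs and the 2-log10 detection limit are assumptions.

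| Day set | Assumed log10 SDs | Raw means | log10 means |
|---|---|---|---|
| Same-day pairs, no detection limit | person 1, day 0.7–1.5, swab 0.3 | 85–94% | above 99% |
| Same | swab 0.5 | 45–60% | 85–87% |
| Same | swab 0.8 | 24–27% | 48–50% |
| All positive swabs, 2-log10 limit | day 1, swab 0.5 | about 50% | 67–70% |
| Same | small SDs (person 0.3, day 0.5, swab 0.3) | 97.5% | 99.8% |
| Same | swab 1 | 20.5% | 24% |
| Days with either swab positive, undetected = 0, log10(x+1) | day 1, swab 0.5 | 54% | 83% |
| SAP's discordant days, swabs correlated | 0–1.2 people have both means | about 0 | about 0 |
| SAP's discordant days, independent detection | about 17 people have both means | 20–29% | 12–22% |

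The widest gap is 85 − 45 = 40 points; the narrowest on a usable day set is 99.8 − 97.5 = 2.3 points. For all positive swabs (day SD 1, swab SD 0.5), about 80% power needs about 50 participants on log10 (82%) and 70 to 80 on raw means (76% and 83%).

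**Larger effects.** For a 90% reduction, power is 88–100% raw and 94–100% log10, so the scale matters little in most settings.

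**Type I error.** On same-day pairs with no effect: 4.6% raw, 5.6% log10, both near nominal. On the SAP's discordant days with independent detection, fewer post-positive days and no copy-number effect, raw means give 6–9% and log10 about 5%.

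**The case against.** The strongest objection is that the gains above belong to day sets the SAP does not use. It averages days positive only before application and subtracts days positive only after, so before and after values come from different days and same-day positives are excluded. On that rule log10 buys nothing: few or no people have both means if the two swabs are correlated, and with independent detection log10 does no better than raw. This stands, and it decides the order of the fix.

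A reader might therefore infer too much in three ways:
- *That a change of scale repairs the endpoint whichever days are used.* The SAP's own day set contradicts this. The gain appears on positive asymptomatic swabs, the Protocol 9.5.2 definition, or on same-day pairs.
- *That one swab sets every person's value.* With 2.24 expected positive days, about 30% of shedders have a single one, and in the others the largest swab dominates without being the whole sum. The sign of each difference still reflects the direction of the effect.
- *That the change is free.* The target moves from arithmetic mean (total load) to geometric mean (typical load), and an undetected swab has no logarithm.

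The objection is also right that the SDs are assumed, that the 50% is borrowed from the detection-rate endpoint, and that the 98% figure concerns bench and animal transmission. What it does not answer is that neither document names a scale other than the plain mean, and that correcting the day set alone would leave the raw-scale loss in place.

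**Conclusion.** The point holds in a limited form. The SAP specifies a raw arithmetic mean per person for an effect described as a percentage. Once the day set follows Protocol 9.5.2 or same-day pairs, log10 means have more power for a proportional reduction. For a 50% reduction in 40 participants the gain is about 0 to 40 points. It is small when swab noise is low or the reduction is large, and absent on the SAP's literal discordant days. The direction rests on copies varying by factors of ten between days; the size rests on SDs, a detection limit and a heterogeneity model that the documents do not supply.

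This is a worthwhile, inexpensive improvement to a secondary endpoint with no stated power. It does not touch the SADE analysis or the primary safety conclusion.

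**What to change.** 1. **Settle the days first.** Reconcile the copy-number hypotheses in SAP 1.3 and the definitions in 4.2.1 and 4.2.2 with Protocol 9.5.2. Use either all positive asymptomatic swabs or same-day before/after pairs, and state what happens to a participant with values on one side only. Setting an absent mean to zero is not a solution: in the simulation with no copy-number effect but fewer post-positive days, it rejected in 29–33% (raw) and 39–40% (log10) of trials, because it re-tests detection.
2. **Then change the scale.** In SAP 4.2.1 and 4.2.2, and for consistency Protocol 9.6, replace the mean copy number with each participant's mean of log10 copies. Keep the signed-rank test on the within-person difference.
3. **Prespecify a detection-limit rule** if undetected swabs can enter, with a sensitivity analysis under an alternative value.
4. **Report** the back-transformed after/before ratio (percent reduction) with a 95% CI, for example from the Hodges-Lehmann estimate of the within-person log10 differences. The raw-scale summary can stay as a descriptive table.

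Cost: document wording only, with no new swabs or participants. The price is a geometric-mean target in place of an arithmetic one, and some dependence on the detection-limit rule.
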